### 7.3 Lost to Follow-Up

A participant will be considered lost to follow-up if he or she fails to return for scheduled visits and is unable to be contacted by the study site.

The following actions must be taken if a participant fails to return to the clinic for a required study visit:

- The site must attempt to contact the participant and reschedule the missed visit as soon as possible, counsel the participant on the importance of maintaining the assigned visit schedule, and ascertain if the participant wants to or should continue in the study. Every effort will be made to undertake a final examination visit as soon as possible and perform all procedures of the End-of-Study visit.
- Before a participant is deemed “lost to follow-up”, the Investigator or designee must make every effort to regain contact with the participant. Contact attempts should be documented in the participant’s medical record.
- Should the participant continue to be unreachable, he/she will be considered to have withdrawn from the study.

## 8 Study Assessments and Procedures

Study assessments and procedures and their timing are summarized in the Schedule of Activities (Section 1.3). Details are given in the following paragraphs.

Adherence to the study design requirements, including those specified in the Schedule of Activities, is essential and required for study conduct.

No protocol waivers or exemptions are allowed.

Immediate safety concerns should be discussed with the Sponsor immediately upon occurrence or awareness to determine if the participant should continue or discontinue study intervention.

## Pre-screening

Study participants will be selected from communities living in the regions of departments of Biankouman and Man in the Tonkpi region, as well as Facobly and Kouibly in the Guémon region, Man, Ivory Coast and around the shores of Lake Victoria around Homa Bay and Mbita in Homabay County, Kenya. Prior to study onset, a list of all children 3 months to 6 years of age living in the selected areas will be prepared using records obtained from the latest census. At study beginning, the households in the villages will be informed about the study through community meetings. Prior to performing any study assessments that are not part of routine medical care, the Investigator or an appropriate designee (if local regulations permit) will obtain written pre screening consent from one of the parents or the guardian/legally authorized representative of the potential participant to allow the diagnostic activities and the identification of schistosomiasis infected children, as described in [Appendix 2](#).

Parents or guardians/legally authorized representatives of participants will be provided with plastic containers labeled with unique identification numbers (IDs) at the first day of pre screening. Parents or guardians/legally authorized representatives of children 3 to < 24 months of age will be provided with urine collecting bags specifically designed for babies. They will be instructed to collect stool and urine samples of the child, each in one of the two separate containers. Stool and urine samples may not be processed on the same day.

### Pre screening diagnosis of S. mansoni infected participants (Cohorts 1 to 3)

Pre screening diagnosis of S. mansoni infection will be done using a single POC-CCA urine cassette test. POC CCA cassettes will be classified as either positive or negative, according to the manufacturer's instructions, with further stratification depending on the strength of the color reaction. Thus, positive cassettes will be classified as + 1 (when result line is easy to see but still weak), + 2 (when result line is dark, but lighter than the control line) or + 3 (when result line is as dark as or darker than the control line). Participants who are positive in the POC-CCA test will be further screened with the aim of:

- Assessing S. haematobium co-infection using the urine filtration technique. A urine sample (about 10 mL) will be filtered through a filter mesh, and the mesh will then be examined under the microscope for S. haematobium egg count. A diagnosis of S. haematobium is defined as positive egg count of S. haematobium in urine ( $> 1$  egg/10 mL of urine) according to WHO classification (WHO, Geneve, Switzerland, 2002) light ( $< 50$  eggs/10 mL of urine) and heavy ( $\geq 50$  eggs/10 mL of urine) infections. Per Section [5.2](#) (Exclusion Criteria), a child infected with both S. mansoni and S. haematobium cannot participate in this study.
- Assessing infection intensity at baseline using the Kato-Katz method: One stool sample will be collected during the pre screening period (Day -28 to Day -1) and the second one within a maximum of 5 days thereafter as baseline. In case the stool collection will not be possible within a maximum of 5 days between the samples, 2 other stool samples could be collected again (maximum 3 times over 28 days). Three Kato-Katz thick smears (41.7 mg) will be prepared from each of the stool samples. Infection intensity (expressed as egg count per gram of stool [epg]) will be calculated for each individual. A diagnosis of S. mansoni is defined as positive egg counts of S. mansoni in stool ( $> 1$  egg/1 occasion) according to the WHO

classification: light (1 to 99 eggs per gram of feces), moderate (100 to 399 eggs per gram of feces) and heavy ( $\geq 400$  eggs per gram of feces) infections.

#### Pre screening diagnosis of *S. haematobium* infected participant (Cohort 4)

The pre screening diagnosis for *S. haematobium* infected participants will take place in a geographical area where the prevalence of this parasite is expected to be high and the prevalence of *S. mansoni* low. As *S. haematobium* and *S. mansoni* co-infected children will not be included in this study (see above), children will provide:

- A stool sample from which two Kato-Katz thick smears (41.7 mg) will be prepared and observed under a microscope to assess *S. mansoni* infection, defined as positive egg counts of *S. mansoni* in stool ( $> 1$  egg/1 occasion).
- Three urine samples to assess *S. haematobium* infection with the urine filtration technique. The first sample will be collected during the pre screening period (Day -28 to Day -1) and the second and the third one within a maximum of 5 days thereafter as baseline. In case the urine collection will not be possible within a maximum of 5 days among the samples, 3 other urine samples could be collected again (maximum 3 times over 28 days). Each urine samples (about 10 mL) will be filtered through a filter mesh, and the mesh will then be examined under the microscope for *S. haematobium* egg count (see above for infection classification). One positive sample out of three is sufficient for a positive diagnosis.

CCI

At the pre screening visit, a Rapid Diagnostic Test (RDT) to detect malaria infection (one blood sample collected by finger puncture) can be performed at investigator's discretion. Treatment of malaria will be undertaken according to national guidelines.

At the pre screening visit, the following data will be collected: date of birth, date of pre screening consent signature, gender and race.

#### **Screening**

Children who have tested positive for *S. haematobium* (only) and children who have tested positive for *S. mansoni* (only), together with one of their parents or guardians/legally authorized representatives, will be invited to the study hospital.

Prior to performing any study assessments that are not part of routine medical care, the Investigator or an appropriate designee (if local regulations permit) will obtain written informed consent as specified in [Appendix 2](#) to allow participation in the study and the completion of the study procedures, from one of the parents or a guardian/legally authorized representative of the participant.

Procedures conducted as part of the participant's routine medical care (e.g., blood count) and obtained before signing of the ICF may be used for screening or baseline purposes, provided the

procedures met the protocol-specified criteria and were performed within the time frame defined in the Schedule of Activities (see Section 1.3).

During the screening period, the following tests/information-gathering will be performed within a maximum of one week prior to treatment initiation:

- Clinical safety laboratory evaluations: haematology, biochemistry and urinalysis. All biological assessments will be performed in a fasted condition, if possible, except for breast-fed babies.
- A Rapid Diagnostic Test (RDT) to detect malaria infection (one blood sample collected by finger puncture). This procedure might be performed either in the hospital or in the village, for operational purposes.
- Demographic data, consisting of date of birth, gender and height
- Medical history, including occurrence of seizures, and consisting of all previous diseases considered relevant (relevant is defined as needing medical treatment for at least 1 week) by the Investigator.
- All previous medications received within the last 6 months as considered relevant by the Investigator (relevant is defined as prescribed to treat a relevant disease as described above)
- Complete physical examination (see Section 8.2.2) including body weight
- Vital signs in supine position (see Section 8.2.3) including:
  - BP (systolic and diastolic) – to be assessed at least 5 minutes after resting
  - Pulse rate – to be assessed at least 5 minutes after resting
  - Body temperature. This procedure might be performed either in the hospital or in the village for operational purposes.

All observed AEs and Concomitant Medications will be reported in the CRF.

Food will be provided within one hour from dosing.

All screening evaluations must be completed and reviewed to confirm that potential participants meet all eligibility criteria. The Investigator will maintain a screening log to record details of all participants screened, to confirm eligibility, and if applicable, record reasons for screening failure.

### **Treatment period**

Participants will be hospitalized from the morning of dosing until at least 12 hours after Study Intervention administration. During this time, participants will be monitored for AEs by study site staff.

In case several assessments are planned at the same time point, the PK samples will be taken at the pre-defined time point. Vital signs will be recorded before PK samples.

## Pre dose assessments

Participants will undergo physical examination, vital signs assessment and re check of eligibility criteria. If assessments have been done on the same day they do not need to be repeated. PK samples will be taken immediately prior to dosing.

## Post dose assessments

PK samples will be taken according to the sampling scheme (see Sections 1.3 and 8.5). The allowed deviation from the pre-specified assessment will be  $\pm 10\%$  (in minutes) of the scheduled time point. In case several assessments are planned at the same time point, the PK samples will be taken at the pre-defined time point.

Vital signs will be recorded 8 hours after first dosing and again at the end of confinement (12 to 24 hours after dosing), when a physical examination will also be performed.

Clinical safety laboratory evaluations (i.e., hematology, biochemistry and urinalysis) (Section 8.2.4) will be conducted 12 hours after dosing. All biological assessments will be performed in a fasted condition if possible, except for those in breast-fed infants.

The maximum amount of blood collected from each participant over the duration of the study, including any extra assessments that may be required, will not exceed 17 mL (see [Appendix 6 Pharmacokinetic Blood Sampling](#)). Repeat or unscheduled samples may be taken for safety reasons or for technical issues with the samples.

In case the participant, due to logistical or social reasons, will have to spend an additional night in the hospital, the end of confinement will be documented and the additional night will not be considered as part of confinement. As such, it will not qualify as an SAE, as described in [Appendix 3](#).

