### Weight

3. Have a minimum body weight of 8.0 kg in 2 to 6 years of age children and 5.0 kg in 3 months to < 24 months of age infants and toddlers

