## **5.4 Screen Failures**

This study includes both a pre screening visit between Day -28 and Day -1, and a screening visit between Day -7 and Day -1.

Participants who fail at the pre screening visit may be pre screened again; they will be assigned a new participant number at the time of the second pre screening visit.

Individuals who pass pre screening but at the time of the planned screening visit:

1. Have consumed grapefruit or grapefruit juice 24 hours prior to enrollment
2. Have been breast-fed by mothers/wet nurses treated with PZQ in the 3 days prior to enrollment
3. Have any other condition that can be normalized within the screening window

can be enrolled as soon as the temporal exclusion criterion does not apply anymore, and as long as the screening window is respected, without any need of being rescreened.

Individuals who pass pre screening but at the time of the planned screening visit:

4. Have been treated within 2 weeks prior to enrollment with anti-malarial medication or drugs that might affect the metabolism of PZQ
5. Are in need of anti-malarial medications
6. Have any other condition that can be normalized within the pre screening window of 28 days

may be rescreened at Investigator's discretion as soon as the temporal exclusion criterion does not apply anymore, and as long as the 28-day window between pre screening and enrollment is respected.

If the second screening visit is not possible to be performed within the original screening visit window (Day -7 to Day 1) then all procedures of the Screening Visit (except for the signature of another screening consent) must be repeated using the same participant screening number. Note that tests requiring additional blood may be repeated as long as the overall blood volume drawn within 4-week period does not exceed 3% of the total blood volume. Therefore, per study protocol no additional blood drawings are allowed in children below 7 kg within the 4-week period.

In this case, the same participant screening number can be kept. If the interval to the proposed Study Intervention dosing would fall outside of the 28-day window, then both pre screening and screening activities have to be repeated, and a new participant number has to be assigned.

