### **8.2.4 Clinical Safety Laboratory Assessments**

Blood and urine samples will be collected for the clinical laboratory tests listed in Appendix 5, at the time points listed in the Schedule of Activities (Section 1.3). All samples should be clearly identified.

Additional tests may be performed at any time during the study, as determined necessary by the Investigator or required by local regulations.

The tests will be performed by the local laboratory.

Samples for the urine, haematology and biochemistry tests will be collected in a fasted condition if possible (except for breast-fed infants), and performed by the local laboratory. Detailed information is given in the Study Procedure Manual.

The Sponsor must receive a list of the local laboratory normal ranges before shipment of study intervention(s). Any changes to the ranges during the study must be forwarded to the Sponsor.

The Investigator must review each laboratory report, document their review, and record any clinically relevant changes occurring during the study in the AE section of the eCRF. The laboratory reports must be filed with the source documents.

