## 8.5 Pharmacokinetics

To get information on systemic plasma concentrations after administration of the final L-PZQ ODT formulation in the targeted pediatric age groups, a subgroup of up to 20 participants 4 to 6 years of age (Treatment group 1a), up to 15 participants 2 to 3 years of age (Cohort 2), between 5 and 10 participants 3 to <24 months of age (Cohort 3) are needed to supply blood samples for determinations of systemic concentrations of R-(-)-PZQ (and if applicable its metabolites). PK sampling from up to 15 participants in Treatment Group 1b will provide information on the systemic plasma concentrations observed after Biltricide administration. For Cohort 4, 15 participants infected with *S. haematobium* (Cohort 4) are needed to supply blood samples for determination of systemic concentrations of R-(-)-PZQ (and if applicable its metabolites). PK sampling from an additional 15 participants will be collected for the 60 mg/kg dose group in Cohort 4. A separate written informed consent will be obtained for PK sampling. Only participants with minimum hemoglobin of 10 g/dL will be asked to take part in the PK sub-study.

Blood samples of approximately 1 mL per time point will be collected for measurement of plasma-concentrations of R-(-)-PZQ (or rac-PZQ) and, if applicable, of its metabolites, immediately prior to dosing (pre dose) and thereafter (post-dose), up to 12 hours after dosing, as specified in the Schedule of Activities (Section 1.3). Instructions for the collection and handling of biological samples will be provided by the Sponsor. The actual date and time (24-hour clock time) of drug administration and each sample will be recorded in the eCRF.

As the known variability of systemic PZQ concentrations and PK parameters is high in adults, the number of participants in each PK subgroup is not based on statistical considerations but on feasibility assessments. Children weighing 5 kg to less than 7 kg will have 4 PK samples taken, children weighing 7 kg to less than 10 kg will have 7 PK samples taken, and children weighing 10 kg and above will have the full PK sampling scheme with 9 PK samples taken. For background information please see "[Appendix 6 Pharmacokinetic Blood Sampling](#)". Participants assigned to the PK sub study should fast between the dosing and 4h post dosing.

**Table 3** PK sampling times per body weight group

| Body weight range (kg) | Sampling times (hours) |           |   |   |   |   |   |   |    |   |

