**Appendix 6      Pharmacokinetic Blood Sampling**

The European Commission Expert Group (Ethical Considerations for clinical studys on medicinal products conducted with minors, Revision Sep 2017), in its recommendation for blood sampling in paediatrics, states that the total blood volume in paediatrics is estimated at 80 mL per kg of bodyweight. Blood loss should not exceed 3% of the total blood volume over 4 weeks, and should not exceed 1% at any single time. With this recommendation in mind, the following table was created, to summarize and ensure that the amount of blood taken from the children enrolled in this study is not excessive, and is within the recommended range.

| Body Weight Range (kg) | Approx. Age | Total blood volume @ 80 ml/kg | 3 % Volume (mL) | 1 % Volume (mL) |
|------------------------|-------------|-------------------------------|-----------------|-----------------|
| 6 ± 1.5 kg             | 3 months    | 480                           | 14.4            | 4.8             |
| 9 ± 1.5 kg             | 10 months   | 720                           | 21.6            | 7.2             |
| 12 ± 1.5 kg            | 2 yrs       | 960                           | 28.8            | 9.6             |
| 15 ± 1.5 kg            | 4 yrs       | 1200                          | 36              | 12              |
| 18 ± 1.5 kg            | 5 yrs       | 1440                          | 43.2            | 14.4            |
| 21 ± 1.5 kg            | 6 yrs       | 1680                          | 50.4            | 16.8            |
| 24 ± 1.5 kg            | 8 yrs       | 1920                          | 57.6            | 19.2            |

The Kenyan health authority KEMRI issued a guidance 2008, stating that the volume drawn for research purposes in addition to volume needed for routine care, should not exceed 1 mL/kg, and the maximum cumulative draw volume allowed is 5 mL/kg within 8 weeks. Source: <http://www.who.int/bulletin/volumes/89/1/BLT-10-080010-table-T2.html>

The present study includes the following sampling:

| Body Weight Range (kg) | Minimum Total blood volume @ 80 ml/kg | 3 % Volume (mL) | Volume Routine Care (mL) | Volume PK (mL) | Volume Total (mL) |
|------------------------|---------------------------------------|-----------------|--------------------------|----------------|-------------------|

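### Appendix 6 prints a 3% blood-loss limit of 14.4 mL beside a 400 mL (5 kg) blood volume, where 3% is 12.0 mL, and the flat 17 mL maximum and repeat-sample sentence in Section 8 do not correct it for the smallest infants

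*Protocol*

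**What the plan says.** Protocol Appendix 6 takes total blood volume as 80 mL per kg and adopts the rule "Blood loss should not exceed 3% of the total blood volume over 4 weeks, and should not exceed 1% at any single time". Its second table applies this to the study. The row for children up to 7 kg lists a minimum blood volume of 400 mL, a 3% volume of 14.4 mL, 8 mL of routine blood and 4 mL for PK, 12 mL in all.

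These are eligible weights. Section 5.1 sets the minimum at "5.0 kg in 3 months to < 24 months of age infants and toddlers", and Section 8.5 says "Children weighing 5 kg to less than 7 kg will have 4 PK samples taken".

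Section 8, Post dose assessments, gives one maximum for every participant: the blood collected over the study, "including any extra assessments that may be required, will not exceed 17 mL", with a pointer to Appendix 6. The next sentence reads "Repeat or unscheduled samples may be taken for safety reasons or for technical issues with the samples". It has no weight condition and cites no other section.

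The weight rule for repeats is in Section 5.4, Screen Failures. Tests may be repeated only if the "overall blood volume drawn within 4-week period does not exceed 3% of the total blood volume", and the section concludes that, per study protocol, "no additional blood drawings are allowed in children below 7 kg within the 4-week period".

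**The concern.** The table exists to show that the blood taken from these children stays within a stated ethical limit. In the band with the least blood to spare, the printed limit is too high, which is the unsafe direction.

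Someone at a site deciding whether to redraw a lost post-dose PK sample would look in Section 8. That section gives a maximum that does not scale with weight, a pointer to the table with the wrong cell, and a general permission to repeat. Nothing on that route mentions the rule for children under 7 kg, which is filed under screen failures. What is at stake is a small excess over the protocol's own blood-loss limit in the lightest infants. No efficacy estimate is involved.

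**Working it through.** **Inputs.** 80 mL/kg and 3% over 4 weeks (Appendix 6); minimum weight 5.0 kg for ages 3 to under 24 months (Section 5.1); routine and PK volumes by band (Appendix 6); 4 mL per safety blood draw (Appendix 4); about 1 mL per PK sample (Section 8.5); 17 mL maximum (Section 8).

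**Formulas.** Implied weight = blood volume / 80. The 3% limit = 0.03 × blood volume, or 0.03 × 80 = 2.4 mL/kg.

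**Reproducing the tables.** The formula gives all seven rows of the first Appendix 6 table; for example, 6 kg gives 480 mL and 14.4 mL. For the sampling table:

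| Weight band | Blood volume printed (mL) | Implied weight (kg) | 3% printed (mL) | 3% recomputed (mL) | Planned total (mL) | Planned, % of printed volume |
|---|---|---|---|---|---|---|
| Up to 7 kg | 400 | 5.0 | **14.4** | **12.0** | 8 + 4 = 12 | 3.00 |
| 7 to under 10 kg | 560 | 7.0 | 16.8 | 16.8 | 8 + 7 = 15 | 2.68 |
| 10 kg and over | 640 | 8.0 | 19.2 | 19.2 | 8 + 9 = 17 | 2.66 |

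Only the lowest band fails. Since 14.4 / 0.03 = 480 mL, the printed figure is the 6 kg value. At 5 kg, 14.4 mL is 14.4 / 400 = 3.6%. A PDF-reading fault is unlikely: 400 is exactly 80 × 5.0 kg, and 14.4 is a genuine entry in the neighbouring table.

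**Headroom at 5 kg.** As printed, 14.4 − 12 = 2.4 mL. Correctly, 12.0 − 12 = 0 mL.

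**The flat maximum.** 17 / 400 = 4.25% at 5 kg. It meets 3% only from 17 / 2.4 = 7.08 kg.

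**One redraw in a 5 kg PK infant, relying on the table.** A 1 mL PK redraw gives 12 + 1 = 13 mL. That is under the printed 14.4 mL but is 13 / 400 = 3.25%. It passes 3% below 13 / 2.4 = 5.42 kg.

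**One repeated safety draw in a 5 kg infant outside the PK subset.** 8 + 4 = 12 mL, or 3.0%, so the limit is reached but not passed.

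**If Section 5.4 is applied.** No extra draw occurs below 7 kg. The 17 mL maximum then exceeds 3% only from 7.00 to 7.08 kg, by at most 17 − 16.8 = 0.2 mL.

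**The case against.** The strongest reply is that the protection already exists. Section 5.4 words its ban below 7 kg as a rule of the study protocol, and the amendment summary shows that blood-volume text was added to that section on purpose. A specific ban should govern over a general permission. Appendix 6 also states 80 mL/kg and 3% in words above the table. It cites a Kenyan limit of 1 mL/kg for research blood, which at 5 kg is 5 mL: four PK samples and one redraw. All of this stands, so the documents do not support saying that the protocol authorises more than 3%. What remains is the wrong cell, a maximum that does not scale with weight, and a missing cross-reference.

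Four stronger readings are tempting and should be resisted.

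- **A 4 mL repeat safety draw in a 5 kg PK infant, giving 16 mL or 4.0%.** This does not follow from the wrong cell, because 16 mL exceeds even the printed 14.4 mL. The table as it stands would stop it.
- **The top band as a second safety error.** Its 640 mL and 19.2 mL agree with each other. They belong to 8 kg, while 10 kg gives 800 mL and 24.0 mL, so the printed limit is conservative.
- **Section 8.2.4 as a licence for more blood.** It says "Additional tests may be performed at any time during the study, as determined necessary by the Investigator or required by local regulations". That sentence covers urine tests as well as blood and does not set aside any volume limit.
- **Scheduled sampling in breach.** Planned venous draws come to at most 3.00%, reached only at 5 kg. Malaria finger-pricks of 20 to 50 µL each, at most two (0.02 to 0.10 mL in all), would bring this to 3.005% to 3.025%. That is trivial beside volumes stated as approximate.

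**Conclusion.** The cell is wrong: 14.4 mL should be 12.0 mL, and a PK infant at the 5.0 kg floor has no headroom. The flat 17 mL maximum does not enforce the protocol's own 3% rule below 7.08 kg. The repeat-sample sentence leaves out the Section 5.4 ban that closes most of that gap.

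The practical size is small. The overshoot attributable to the cell is one 1 mL PK redraw in a child under 5.42 kg: 13 mL against 12.0 mL at 5 kg, and only if Section 5.4 is overlooked. Section 8.5 plans 5 to 10 PK children in Cohort 3. The documents do not say how many PK children in Cohorts 3 and 4 will weigh under 7 kg, and there may be none.

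Severity is minor. The arithmetic rests on the protocol's 80 mL/kg and on its approximate sample volumes. Sampling times, eligibility, sample size and efficacy analysis do not change.

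**What to change.** 1. In the lowest band of the Appendix 6 sampling table, change 14.4 to 12.0.
2. In Section 8, keep 17 mL as the maximum for the whole study and add that blood drawn in any 4-week period must not exceed 2.4 mL/kg (12.0 mL at 5 kg, 14.4 mL at 6 kg, 16.8 mL at 7 kg). The new limit should be added to the 17 mL and should not replace it, so that the whole-study maximum is not loosened.
3. Make the repeat-sample sentence in Section 8 subject to Section 5.4, so that redraws for technical reasons are not allowed below 7 kg. Section 5.4 has no exception at present. If one is written, limit it to draws needed for the child's immediate safety.

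Relabelling the top band with its 10 kg values (800 and 24.0 mL) is optional and has no safety effect.

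The cost is one table cell, an edit to two sentences and a note to sites. A few PK or non-urgent laboratory values may be lost in the smallest infants because a failed sample cannot be redrawn, but Section 5.4 already implies that loss.
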